2.4.6 Analyses of pharmacokinetic variables

Serum concentrations of efpeglenatide, pre-dose (C_{trough}) and post-dose, will be summarized (mean, SD, CV%, median, minimum, and maximum) over time and by treatment. All below quantitation limit (BLQ) concentration will be treated as zero and all missing concentrations will be treated as missing for descriptive statistics.

Serum concentrations of efpeglenatide, pre-dose (C_{trough}) and post-dose, will be listed.

Population PK analysis will be discussed in a separate analysis plan.

2.4.7 Analyses of quality of life/health economics variables

Not Applicable.

2.5 DATA HANDLING CONVENTIONS

2.5.1 General conventions

The following formulas will be used for computation of parameters.

Demographic formulas

The participant's duration of diabetes (years) is calculated using the date of informed consent and the date of diabetes diagnosis.

If date of diabetes diagnosis is a complete date, then the duration of diabetes is (date of informed consent - date of diabetes diagnosis + 1) / 365.25. If date of diabetes diagnosis is a partial date:

- Year and month are not missing, but day is missing, then day = 01
- Year is not missing, but month and date are both missing, then month = January and day = 01.

Renal function formulas

eGFR will be calculated using the 4-variable Modification of Diet in Renal Disease (MDRD-4) formula below (1):

- $eGFR \text{ (mL/min/1.73 m}^2\text{)} = 175 \times \text{serum creatinine (mg/dL}}^{-1.154} \times \text{Age(year}}^{-0.203} \times 1.212$
[if black] $\times 0.742$ [if female]

2.5.2 Data handling conventions for secondary efficacy variables

No special data handling.

2.5.3 Missing data

For categorical variables, participants with missing data are not included in calculations of percentages unless otherwise specified. When relevant, the number of participants with missing data is presented.

Derived variables will be considered missing if any of the original variables required to calculate them are missing. For example, if either a baseline assessment or an endpoint assessment is missing for a particular participant, then change from baseline at endpoint will be missing. Depending upon the assessment, analyses may not include all participants in the analysis population, because certain participants in the intended population may have missing data.

Handling of computation of treatment duration if investigational medicinal product end of treatment date is missing

For the calculation of the treatment duration, the date of the last dose of IMP is equal to the date of last administration reported on the treatment status case report form page. If this date is missing, the exposure duration should be left as missing.

In the definition of the whole on-treatment period, the date of the last dose of IMP is equal to the date of the last administration reported on the treatment status case report form page. If this date is missing, the date of the last IMP injection in the exposure page will be used for participants with at least 1 injection or the date of visit 3/randomization visit will be used for participants who were lost to follow-up after the initial dispensation of IMP.

Handling of medication missing/partial dates

No imputation of medication start/end dates or times will be performed. If a medication date or time is missing or partially missing, and it cannot be determined whether it was taken prior or concomitantly, it will be considered a prior, concomitant, and post-treatment medication.

For time to event (TTE) analysis, partial rescue medication dates will be imputed using the following rules:

- If year and month are not missing, but day is missing, then day = 15
- If year is not missing, but month and date are both missing, then month = June and day = 15.

Note: if it's possible that the partial date is within the whole on-treatment period, but the imputed date falls outside of the whole on-treatment period, then imputed date will be set to the nearest date inside the whole on-treatment period.

Handling of adverse events/hypoglycemia with missing or partial date/time of onset

Missing or partial AE/hypoglycemia onset dates and times will be imputed so that if the partial AE/hypoglycemia onset date/time information does not indicate that the AE/hypoglycemia started prior to treatment or after the whole on-treatment period, the AE/hypoglycemia will be classified as treatment-emergent. No imputation of AE end dates/times will be performed. These data

imputations are for categorization purpose only and will not be used in listings. No imputation is planned for date/time of AE resolution.

Handling of adverse events/hypoglycemia when date and time of first investigational medicinal product administration is missing

When the date and time of the first IMP administration is missing, all AEs/hypoglycemia that occurred on or after the day of randomization should be considered as TEAEs. The exposure duration should be kept as missing.

Handling of missing assessment of relationship of adverse events to investigational medicinal product

If the assessment of the relationship to IMP is missing, then the relationship to IMP has to be assumed and the AE considered as such in the frequency tables of possibly related AEs, but no imputation should be done at the data level.

Handling of missing intensity of adverse events

If the intensity is missing for 1 of the treatment-emergent occurrences of an AE, the maximal intensity on the remaining occurrences will be considered. If the intensity is missing for all the occurrences, a “missing” category will be added in the summary table.

Handling of potentially clinically significant abnormalities

If a participant has a missing Baseline, he or she will be grouped in the category “normal/missing at Baseline.”

For PCSAs with 2 conditions, one based on a change from Baseline value or a normal range and the other on a threshold value, with the first condition being missing, the PCSA will be based only on the second condition.

For a PCSA defined on a threshold and/or a normal range, this PCSA will be derived using this threshold if the normal range is missing; eg, for eosinophils the PCSA is >0.5 GIGA/L or $>ULN$ if $ULN \geq 0.5$ GIGA/L. When ULN is missing, the value 0.5 should be used.

Measurements flagged as invalid by the laboratory will not be summarized or taken into account in the computation of PCSA values.

Handling of missing screening value to derive actual randomization strata

In case of missing data at screening visit for HbA1c and BMI, unscheduled data before randomization visit can be used. If the sample is confirmed as being for the purpose of a re-screen, then the result is sent to be integrated into IRT. In case of several data collected, the earliest is used.

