### 3 OBJECTIVES AND ENDPOINTS

**Table 1 - Objectives and endpoints**

Objectives	Endpoints
Primary  To demonstrate the superiority of once-weekly injection of efpeglenatide 2, 4, or 6 mg in comparison to placebo in HbA1c change from baseline to Week 30 in participants with T2DM inadequately controlled with diet and exercise	

Change from baseline to Week 30 in HbA1c

Secondary  To demonstrate the superiority of once-weekly injection of efpeglenatide 2, 4, and 6 mg in comparison to placebo on glycemic control  To demonstrate the superiority of once-weekly injection of efpeglenatide 2, 4, and 6 mg in comparison to placebo on body weight  To evaluate the safety of once-weekly injection of efpeglenatide 2, 4, and 6 mg	

Number of participants with HbA1c <7% at Week 30

Change from baseline to Week 30 in fasting plasma glucose (FPG)

Change from Baseline to Week 56 in HbA1c

Change from baseline to Weeks 30 and 56 in body weight

Number of participants with at least one hypoglycemic event during treatment period

Number of hypoglycemic events per participant-year during treatment period

Number of participants with AEs (see Section 8.3)

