2.4.3 Extent of investigational medicinal product exposure and compliance

The extent of IMP exposure and compliance will be assessed and summarized by actual treatment within the safety population ([Section 2.3.2](#)).

2.4.3.1 *Extent of investigational medicinal product exposure*

The extent of IMP exposure will be assessed by cumulative exposure (patient years), duration (days), and category (weeks).

Duration of IMP exposure is defined as last dose date – first dose date + 7, regardless of unplanned intermittent discontinuations (see [Section 2.5.3](#) for calculation in case of missing or incomplete data).

Duration of IMP exposure will be summarized descriptively as a quantitative variable (number, mean, SD, median, minimum, and maximum). In addition, duration of treatment exposure will also be summarized categorically by numbers and percentages for each of the following

categories and cumulatively according to these categories: 1 to 2 weeks, 3 to 4 weeks, 5 to 8 weeks, 9 to 12 weeks, 13 to 18 weeks, 19 to 24 weeks, 25 to 30 weeks, 31 to 43 weeks, 44 to 56 weeks, and >56 weeks. The duration of treatment exposure in weeks will be the duration (in days)/7, rounded to the nearest integer.

Duration of study will be summarized separately and analyzed descriptively as a quantitative variable (number, mean, SD, median, minimum, and maximum). The duration of study is defined as date of completion or discontinuation – date of first dose of IP + 1. In the case of not treated participants, the randomization date will be used for calculation purposes.

2.4.3.2 *Compliance*

A given administration will be considered noncompliant if the participant did not take the planned dose of treatment as required by the protocol. No imputation will be made for participants with missing or incomplete data.

Percentage of compliance for a participant will be defined as the number of injections (partial injection will be counted as 1 injection) that the participant was compliant divided by the total number of injections that the participant was planned to take during the treatment period defined from the first to the last dose injection. Number of planned injections is calculated as following:

$$1 + (\text{last dose date} - \text{first dose date} + 1) / 7, \text{ rounded to the nearest integer.}$$

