2.4.5.2 Analysis of hypoglycemia

Treatment-emergent hypoglycemia events will be tabulated separately from the AEs.

Event frequency and incidence of hypoglycemia events will be summarized by treatment for all reported hypoglycemia and per type of hypoglycemic event described in [Section 2.1.4.5](#) (ie, severe, documented symptomatic, asymptomatic, probable symptomatic, relative) for safety population. Incidence of severe or documented symptomatic hypoglycemia events will be summarized by study period (≤ 4 weeks (titration period), >4 weeks to ≤ 8 weeks, >8 weeks to ≤ 30 weeks, >30 weeks) and according to time of occurrence (nocturnal [ie, 00:00 to 05:59 am], daytime [ie, 06:00 am to 23:59]) for safety population. Documented hypoglycemia (symptomatic or asymptomatic) will be also evaluated for the more stringent plasma glucose threshold of <54 mg/dL (3.0 mmol/L), as well as for ≥ 3.0 and <3.9 mmol/L (≥ 54 and <70 mg/dL). Frequency and percentage of participants with at least one hypoglycemia event will be summarized as well.

Event rate of hypoglycemia per participant year will be calculated by treatment using the total number of hypoglycemia events from all participants (denoted as n) divided by the total exposures from all participants expressed in years (ie, participant exposure in days divided by 365.25, denoted as t). Multiple events from an individual participant will all count. Event rates of hypoglycemia per participant year (all reported hypoglycemia, severe, documented symptomatic, asymptomatic, probable symptomatic, relative hypoglycemia, and documented hypoglycemia with plasma glucose <54 mg/dL [3.0 mmol/L]) will be presented by treatment group for the 30-week core on-treatment period and the whole on-treatment period.

The summary of frequency and event rate in participant years for severe or documented symptomatic hypoglycemia will be provided as appropriate by gender (Male, Female), age group (<50 , ≥ 50 to <65 , ≥ 65 to <75 , ≥ 75 years), and race (Asian, Black or African American, White, Other).

A KM curve will also be provided by treatment group for the time to first severe or documented symptomatic hypoglycemia during the whole on-treatment period.

A listing of participants for all severe or documented symptomatic hypoglycemia events reported on the specific eCRF “Hypoglycemic Event Information” page will be provided and sorted by participants.

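### Participants with a missing first- or last-dose date add hypoglycemia events but no time to the rate per participant-year, biasing it slightly upward

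*SAP*

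**What the plan says.** Protocol Table 1 lists as a secondary safety endpoint: "Number of hypoglycemic events per participant-year during treatment period". SAP 2.4.5.2 defines the rate as "the total number of hypoglycemia events from all participants (denoted as n) divided by the total exposures from all participants expressed in years", and event rates "will be presented by treatment group for the 30-week core on-treatment period and the whole on-treatment period".

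Exposure is defined once, in SAP 2.4.3.1. "Duration of IMP exposure is defined as last dose date" minus first dose date plus 7 days, ignoring interruptions.

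SAP 2.5.3 covers missing dates:

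- **Last-dose date missing on the treatment status page, treatment duration:** "If this date is missing, the exposure duration should be left as missing".
- **Same date missing, whole on-treatment period:** "the date of the last IMP injection in the exposure page will be used for participants with at least 1 injection". For participants lost to follow-up after the first dispensation, the Visit 3/randomization date is used.
- **First-dose date missing:** all hypoglycemia from the day of randomization is treatment-emergent, and "The exposure duration should be kept as missing".

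SAP 2.3.2 keeps a participant who was dispensed IMP and then lost without documentation in the safety population as exposed.

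**The concern.** A rate per participant-year is interpretable only if each person who can contribute an event also contributes the time over which that event could occur. For participants with a missing first- or last-dose date, the SAP supplies a date so that events can be classified, then withholds it from the denominator. No rule removes their events from the numerator. The error has one direction: the arm's rate is too high, by more in an arm with more missing dates. Because the affected quantity is a listed secondary endpoint, two programmers following the SAP should not be able to reach different values.

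**Working it through.** The documents give no event count, rate or number of missing dates, so there is no stated figure to reproduce. The check applies the SAP's own definitions.

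**1. Both dates recorded, whole period.** Assume a completer injects weekly at Weeks 0 to 55. The last dose is 55 × 7 = 385 days after the first.

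- Exposure (SAP 2.4.3.1): 385 + 7 = 392 days, or 392/365.25 = 1.073 years.
- Hypoglycemia window (SAP 2.1.4): first injection to 7 days after the last, also 392 days.

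Numerator and denominator match.

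**2. A date missing.** Take 100 participants per arm (SAP 1.3) and a constant event rate. Let k participants have missing exposure, and let f be their true time in the event window as a fraction of full length. Events are proportional to (100 − k) + k·f, while counted time is proportional to 100 − k. The relative inflation is therefore k·f/(100 − k), whatever the rate.

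| k (assumed) | f = 0.5 | f = 1 |
|---|---|---|
| 1 | 0.5/99 = 0.5% | 1/99 = 1.0% |
| 2 | 1/98 = 1.0% | 2/98 = 2.0% |
| 5 | 2.5/95 = 2.6% | 5/95 = 5.3% |

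With an assumed rate of 0.20 per participant-year, k = 5 and f = 1 give 0.20 × 100/95 = 0.2105.

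**3. Participants closed at Visit 3.** Their event window is about 7 days, so f = 7/392 = 0.018. Five of them inflate the rate by 5 × 0.018/95 = 0.09%.

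**4. After alignment.** If the same dates feed events and time, counted time is proportional to (100 − k) + k·f as well, and the assumed 0.20 is recovered.

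**5. The 30-week rate.** SAP 2.1.4 ends the core window at Visit 10 (Day 210 if that visit is missing) or 7 days after the last injection, whichever is earlier. No exposure cut at that point is defined. If someone divided core-period events by whole-trial exposure, a completer's rate would be multiplied by 210/392 = 0.536, which is 46% too low. That is the literal worst case only.

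**The case against.** The strongest reply is that this is an edge case.

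- Protocol Table 2 requires the date of each injection to be recorded, Protocol 7.1 requires IMP discontinuation to be fully documented in the e-CRF, and the first dose is given on site at Visit 3. Missing dates should be few, and a missing first-dose date improbable.
- SAP 2.5.3 says in general terms that analyses may leave out participants with missing data, which could be read as dropping them from both sides.
- SAP 2.4.5 describes the safety analysis as essentially descriptive, and the companion endpoint, the number of participants with at least one event, does not use exposure.

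All of this limits the size. It does not remove the inconsistency: the general sentence competes with specific rules in the same section that keep the events, and with a formula that names all participants on both sides.

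A reader might also infer three stronger points that the documents do not support:

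- **That the endpoint is mismatched as a whole.** Step 1 shows that it is not when both dates are recorded.
- **That arms with more loss to follow-up are necessarily inflated.** Nothing equates loss to follow-up with a blank last-dose date, and the loss to follow-up that SAP 2.5.3 names is closed at Visit 3, costing about a week per person.
- **That the plan produces a 30-week rate 46% too low.** The core window is defined, and nothing tells the analyst to divide by 56-week exposure. The ordinary reading is exposure within the stated period; what is missing is a sentence saying so.

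**Conclusion.** The inconsistency is real and minor. Followed as written, SAP 2.5.3 and 2.4.5.2 bias the hypoglycemia rate upward through participants with a missing first- or last-dose date, and through no one else over the whole on-treatment period. With 1 to 5 such participants per 100, half- to full-length true exposure and a constant event rate, the inflation in that arm is about 0.5% to 5%; for those closed at Visit 3 it is around 0.1% or less. The number of missing dates is an assumption, because the documents do not give it. The rate is outside the testing hierarchy, so type I error and power are untouched. The absent 30-week denominator is a matter for clarification.

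**What to change.** In SAP 2.4.5.2, for the hypoglycemia rate only, define time at risk from the dates that classify the events: last injection minus first injection plus 7 days. Use the fallback last-dose date of 2.5.3 where that date is missing, and the randomization date where the first-dose date is missing. With no further day added, a completer keeps 392 days, in line with 2.4.3.1. The alternative is to exclude such participants from both numerator and denominator and report how many there are in each arm.

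In the same edit, state that time at risk for the 30-week rate stops at the end of the core window in 2.1.4.

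The product complaint rate in SAP 2.4.5.4 also divides by cumulative exposure. Apply the same fallback dates there, but not the 7-day limit: complaints are counted over the on-treatment period, which outside hypoglycemia runs to 30 days after the last injection.

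Exposure tables may keep missing as missing. The cost is a few sentences in the SAP and one derived variable; the SAP already names the dates needed.

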2.5.4 Windows for time points

Nominal post-baseline visits will be used for descriptive statistics and time course plots.

Display of safety data by visit (laboratory variables and vital signs)

Descriptive statistics (N, mean, SD, minimum, median, maximum) of quantitative laboratory variables and vital signs (observed data and change from baseline) during the whole on-treatment period for all scheduled visits as per protocol will be provided (ie, only including participants having non-missing assessments at a nominal visit). Summaries showing data by visit will be presented according to the visit number and labeled with the targeted approximate day/week.

As specified in the study protocol, laboratory data from scheduled visits are reported by central laboratories. When both central and local laboratories report values from the same blood sample (ie, sample collected at the same date and time), only measurements from the central laboratory will be included in the analyses. When only local laboratory results are reported, and central laboratory results are unavailable, the local results will not be used in the efficacy analyses. In the safety analyses, local results will only be used in the PCSA summary if they are accompanied by a local laboratory normal range.

When a participant has more than 1 measurement from the central laboratory for the same laboratory parameter on the same date, the average of the measurements will be used. For the same laboratory parameter, if a participant has more than one measurement on different dates for the same scheduled visit, the value closest to the scheduled visit will be used for the scheduled visit. When the values for the same scheduled visit are equidistant, the last value should be used for the scheduled visit.

Efficacy data at Week 30/Week 56

The scheduled measurements at the endpoint visit (Week 30 or Week 56) as collected will be used in the efficacy analyses including those obtained after IMP discontinuation and/or introduction of rescue therapy. For participants whose efficacy measurement is not available at the endpoint visit, the measurement at unscheduled visit (including the end of treatment and/or study visit for those prematurely discontinued) will be used if the unscheduled measurement is within +/-30 days (7 days for FPG and SMPG) of the date of the end point visit [targeted study Day 210 for Week 30 (or Day 392 for Week 56)]. If multiple measurements are associated to the same targeted date, the closest to the targeted study day will be used. In case of equality, the last measurement will be used. If there are still no measurement for a given parameter at an endpoint visit, the data is considered missing for efficacy analyses, where multiple imputation would be applied as appropriately as described in [Section 2.4.4.1](#).

Linked adverse events that worsened or became serious

An AE that worsened or became serious will have a separate record in the data from the original event record with a reference identification number that links the new record to the original record. An AE that worsened or became serious will be considered a new recurring AE in the summary of recurrent events or in the summary of events by time intervals.

2.5.5 Unscheduled visits

Unscheduled visit measurements of laboratory data, vital signs, and ECG will not be included in the by-visit summaries but will be used for computation of Baseline and PCSAs.

2.5.6 Pooling of centers for statistical analyses

Not Applicable.

2.5.7 Statistical technical issues

Not Applicable.

3 INTERIM ANALYSIS

No interim analysis is planned.

4 DATABASE LOCK

The database is planned to be locked approximately 4 to 6 weeks after last participant last visit.

5 SOFTWARE DOCUMENTATION

All summaries and statistical analyses will be generated using SAS version 9.3 or higher.

